Summary statistics and a regression model will be used to estimate a distribution of preferences weights for each level of each benefit and harm in the preference survey (described in a SAP). Maximum acceptable risk for harms will be calculated for varying degrees of benefit. Analyses and reporting of these survey results may be reported separately.

TIME AND EVENTS SCHEDULE (Induction Phase)

Phase	Induction Phase ^{a)}								
	1.1 ^{b)}	1.2	1.3	1.4	1.5	1.6	1.7	1.8	1.9
Visit number	1								
Week	1	2	3	4					
Study day	1 (baseline)	4	8	11	15	18	22	25	28
Clinical Study Site visit window (in days)	-	±1	±1	±1	±1	±1	±1	±1	±1
Study Procedures									
Screening/Administrative									
Informed consent (ICF) – performed prior to any study procedure	X								
Inclusion/exclusion criteria-	X ^{c)}								
Study Drug									
Esketamine nasal spray ^{g)}	X	X	X	X	X	X	X	X	
Drug accountability (intranasal study medication)	X	X	X	X	X	X	X	X	
Safety Assessments (Site-completed)									
Physical examination	X ^{c)}								X
Nasal examination ^{c)}	X								X
Vital signs: blood pressure, pulse, respiratory rate, temperature ^{c),g)}	X	X	X	X	X	X	X	X	
Vital signs (postdose): blood pressure, pulse, respiratory rate ^{d),g)}	X	X	X	X	X	X	X	X	
Weight	X								X
12-lead ECG ^{e),g)}	X				X			X	
C-SSRS ^{c),g)}	X	X	X	X	X	X	X	X	X
MOAA/S and pulse oximetry ^{f),g)}	X	X	X	X	X	X	X	X	
CGADR ^{g),h)}	X	X	X	X	X	X	X	X	
Efficacy Assessments (Clinician)									
MADRS (7-day recall) ^{c)}	X		X		X		X		X
CGI-S ^{c)}	X	X	X	X	X		X		X
Subject-completed Assessments									
PHQ-9	X				X				X
SDS	X								X
EQ-5D-5L	X				X				X
TSQM-9	X								X
MAGDA ^{l)}	X				X				X
QLDS	X				X				X
Patient Stated-choice Preference Survey ^{k)}									X ^{l)}
Cognition Testing									
Computerized test battery and HVL T-R ^{c)}	X								X
Clinical Laboratory Assessments									
HbA1c ^{l)}	X								
Hematology, chemistry ^{c)}	X								X
Urine drug screen ^{c)}	X								

Phase	Induction Phase ^{a)}								
	1.1 ^{b)}	1.2	1.3	1.4	1.5	1.6	1.7	1.8	1.9
Visit number	1	2	3	4	5	6	7	8	9
Week	1		2		3		4		
Study day	1 (baseline)	4	8	11	15	18	22	25	28
Clinical Study Site visit window (in days)	-	±1	±1	±1	±1	±1	±1	±1	±1
Alcohol breath test ^{c)}	X								
Urinalysis ^{c)}	X								X
Urine pregnancy test ^{c)} (only for females of child bearing potential)	X				X				X
Ongoing Subject Review									
Concomitant Therapy	Ongoing								
Adverse Events	Ongoing								

Footnotes:

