Concomitant therapy	Ongoing											
Adverse events	Ongoing											

Footnotes:

Abbreviations: CGADR = Clinical Global Assessment of Discharge Readiness; CGI-S = Clinical Global Impression - Severity; C-SSRS = Columbia Suicide Severity Rating Scale; EQ-5D-5L = European Quality of Life (EuroQol) Group, 5-Dimension, 5-Level; EW = Early Withdrawal; 7-item; HbA1c = Hemoglobin A1c; HRUQ = Healthcare Resource Use Questionnaire; HVLTR-R = Hopkins Verbal Learning Test - Revised; MADRS = Montgomery-Asberg Depression Rating Scale; MOAA/S = Modified Observer's Assessment of Alertness/Sedation; PHQ-9 = Patient Health Questionnaire, 9-item; SDS = Sheehan Disability Scale; QLDS=Quality of Life in Depression Scale

Note: On intranasal dosing days, time = 0 is defined as the time of the first intranasal spray. Therefore, “postdose” time points are referenced from this.

- a) Visit window: ±3 days. Clinic visits will be conducted for all intranasal treatment sessions; a remote visit (ie, telephone contact) will be conducted for all other visits with a scheduled study procedure. Due to the variable clinic visit frequency, following Visit 2.4, visit numbers will continue sequentially (eg, 2.5, 2.6, etc) until the subject completes the phase. The frequency of study procedures following Week 4 to the end of the phase is provided within the respective column (ie, every week, 2 weeks, 4 weeks, 8 weeks, 12, and 24 weeks).
- b) The Day 28 visit of 54135419TRD3008 (Visit 1.9) is expected to coincide with Visit 2.1. Results for all predose assessments performed on Day 28 of the induction phase of 54135419TRD3008 (ie, Visit 1.9) will not be repeated as part of Visit 2.1.

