- If a subject's predose SBP is >140 mmHg and/or DBP is >90 mm Hg, it is recommended to repeat the blood pressure measurement after subject rests in sitting or recumbent position. If after rest and repeated measurements, predose SBP is >140 mmHg and/or DBP is >90 mm Hg, then dosing should be postponed and the subject scheduled to return on the following day or within the given visit window. If the blood pressure elevation still persists on the next visit, the subject will be scheduled for a consultation by a cardiologist, other specialist, or primary care physician (PCP) prior to further dosing.
- If at any post-dose time point on the dosing day the SBP is ≥ 180 mmHg but <200 mmHg and/or the DBP is ≥ 110 mmHg but <120 mmHg, further intranasal dosing should be interrupted and the subject should be referred to a cardiologist, other specialist, or primary care physician for a follow-up assessment.

After the assessment by a cardiologist, other specialist, or PCP, if recommended by the referring doctor and considered appropriate according to the clinical judgment for the subject to continue in the study, the subject may continue with intranasal dosing provided the predose blood pressure at the next scheduled visit is within the acceptable range (see bullet point above).

- If at any post-dose time point on the dosing day the SBP is ≥ 200 mmHg and/or the DBP is ≥ 120 mmHg, the subject must discontinue from further dosing and the subject should be referred to a cardiologist, other specialist, or PCP for a follow up assessment.
- During the induction phase, at 1.5 hours postdose, if the SBP is ≥ 160 mm Hg and/or the DBP ≥ 100 mm Hg, blood pressure monitoring should continue every 30 minutes until:
 - the blood pressure is <160 mm Hg SBP and <100 mm Hg DBP, or
 - in the investigator's clinical judgment, the subject it is clinically stable and can be discharged from the study site, or
 - the subject is referred for appropriate medical care if clinically indicated.
 - if the blood pressure remains ≥ 180 mmHg SBP and/or ≥ 110 mmHg DBP, 2 hours after dosing, the subject should be referred for immediate medical treatment.

**Guidance for Blood Pressure Monitoring on Intranasal Treatment Session Days
(Subjects ≥ 65 years of age)**

Given the potential for treatment emergent transient elevation in systolic and diastolic blood pressure, the following guidance should be followed on intranasal dosing days:

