9.2. Safety Evaluations

Details regarding the IDMC are provided in Section 11.7.

Any clinically relevant changes occurring during the study must be recorded on the Adverse Event section of the CRF.

Any clinically significant abnormalities persisting at the end of the study/early withdrawal will be followed by the investigator until resolution or until a clinically stable condition is reached.

The study will include the following evaluations of safety and tolerability according to the time points provided in the Time and Events Schedules.

There may be instances where a subject has started a scheduled clinic visit in which an intranasal treatment session is planned, but due to predose vital sign measurements (eg, blood pressure value), a decision has been made to postpone/delay the intranasal treatment session within the visit window permitted per protocol. In such cases, all time points (including predose) of the following assessments must be repeated on the actual intranasal treatment session day: vital sign (ie, blood pressure, pulse, respiratory rate, and temperature), 12-lead ECG, C-SSRS (since last visit), MOAA/S, and pulse oximetry.

Adverse Events

Adverse events will be reported by the subject (or, when appropriate, by a caregiver, surrogate, or the subject's legally acceptable representative) for the duration of the study. Adverse events will be followed by the investigator as specified in Section 12, Adverse Event Reporting.

Treatment emergent AEs of special interest will be examined separately (please refer to Section 3.2.5 and Section 11.3).

Clinical Laboratory Tests

Blood samples for serum chemistry and hematology and urine samples for urinalysis will be collected. The investigator must review the laboratory results, document this review, and record any clinically relevant changes occurring during the study in the adverse event section of the CRF. The laboratory reports must be filed with the source documents.

The use of local laboratories is allowed in cases where initiation of treatment or safety follow-up is time-critical and the central laboratory results are not expected to be available before the need to begin dosing or if actions need to be taken for safety reasons.

The following tests will be performed by the central laboratory, unless noted otherwise:

- **Hematology panel:**

- | | |
|------------------------|--|
| - hemoglobin | - white blood cell count with differential |
| - hematocrit | - platelet count |

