2.3. Visit Windows

As subjects do not always adhere to the protocol visit schedule, the following rules are applied to assign actual visits to protocol visits. Listed below are the visit windows and the target days for each visit. The reference day is Study Day 1 (which is the first day that any study drug was taken in the induction phase for subjects who enter the study at the induction phase, and the first day any study drug was taken in the optimization/maintenance phase for responders from induction phase and subjects directly entering the optimization/maintenance phase of this study).

If a subject has 2 or more scheduled or unscheduled visits in one visit window, the visit closest to the target day will be used as the protocol visit for that visit window. If 2 actual visits are equidistant from the target day within a visit window, the later visit is used. If a visit window has no scheduled visits but does have unscheduled visits, then the unscheduled visit closest to the scheduled visit will be used.

All assignments will be made in chronological order. Once a visit is assigned to a visit window, it will no longer be used for a later time point except for the end point.

Listed below are the visit windows and the target days (if applicable) for each visit defined in the protocol for all phases (Table 1).

Table 1: Analysis Visits

Parameter	Analysis Phase	Scheduled Day ^a	Time Interval (label on output)	Time Interval ^a (Day)	Target Time Point ^a (Day)
Montgomery-Asberg Depression Rating Scale (MADRS)	IND	1	Baseline	≤ 1	1
		8	Day 8 (IND)	2 - 11	8
		15	Day 15 (IND)	12 - 18	15
		22	Day 22 (IND)	19 - 24	22
		28	Day 28 (IND)	25 to end of IND	28
		IND final visit	End Point (IND)	2 to end of IND	
	OP/MA i=1,2,3,...	1	Baseline (OP/MA)	≤ 1	1
		15	Week 3 (OP/MA)	2 - 32	15
		50	Week 8 (OP/MA)	33 - 64	50
		50 + i*28	Week (8 + i*4) (OP/MA)	37 + i*28 to 64 + i*28	50 + i*28
OP/MA final visit		End Point (OP/MA)	2 to end of OP/MA		
CGI-S	IND	1	Baseline	≤ 1	1
		4	Day 4 (IND)	2 - 6	4
		8	Day 8 (IND)	7 - 9	8
		11	Day 11 (IND)	10 - 13	11
		15	Day 15 (IND)	14 - 18	15

Table 1: Analysis Visits

Parameter	Analysis Phase	Scheduled Day ^a	Time Interval (label on output)	Time Interval ^a (Day)	Target Time Point ^a (Day)
		22	Day 22 (IND)	19 - 24	22
		28	Day 28 (IND)	25 to end of IND	28
		IND final visit	End Point (IND)	2 to end of IND	
	OP/MA i=1,2,3,...	1	Baseline (OP/MA)	≤ 1	1
		8	Week 2 (OP/MA)	2 - 11	8
		15	Week 3 (OP/MA)	12 - 18	15
		22	Week 4 (OP/MA)	19 - 29	22

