		22 + i*14	Week (4 + i*2) (OP/MA)	16 + i*14 to 29 + i*14	22 + i*14
OP/MA final visit	End Point (OP/MA)	2 to end of OP/MA			
Patient Health Questionnaire – 9 item (PHQ-9), EuroQol Group; 5 dimension; 5 level (EQ-5D-5L), Quality of Life in Depression Scale (QLDS)	IND	1	Baseline	≤ 1	1
		15	Day 15 (IND)	2 - 21	15
		28	Day 28 (IND)	22 to end of IND	28
	IND final visit	End Point (IND)	2 to end of IND		
	OP/MA i=1,2,3,...	1	Baseline (OP/MA)	≤ 1	1
		15	Week 3 (OP/MA)	2 - 32	15
		50	Week 8 (OP/MA)	33 - 64	50
		50 + i*28	Week (8 + i*4) (OP/MA)	37 + i*28 to 64 + i*28	50 + i*28
OP/MA final visit	End Point (OP/MA)	2 to end of OP/MA			
Sheehan Disability Scale (SDS)	IND	1	Baseline	≤ 1	1
		28	Day 28 (IND)	2 to end of IND	28
		IND final visit	End Point (IND)	2 to end of IND	
	OP/MA i=1,2,3,...	1	Baseline (OP/MA)	≤ 1	1
		15	Week 3 (OP/MA)	2 - 32	15
		50	Week 8 (OP/MA)	33 - 64	50
		50 + i*28	Week (8 + i*4) (OP/MA)	37 + i*28 to 64 + i*28	50 + i*28
	OP/MA final visit	End Point (OP/MA)	2 to end of OP/MA		
Treatment Satisfaction Questionnaire for Medication (TSQM-9)	IND	1	Baseline	≤ 1	1
		28	Day 28 (IND)	2 to end of IND	28
		IND final visit	End Point (IND)	2 to end of IND	
	OP/MA i=1,2,3,...	1	Baseline (OP/MA)	≤ 1	1
		50	Week 8 (OP/MA)	2 - 64	50
		50 + i*28	Week (8 + i*4) (OP/MA)	37 + i*28 to 64 + i*28	50 + i*28
OP/MA final visit	End Point (OP/MA)	2 to end of OP/MA			
	IND	28	Day 28 (IND)	1 to end of IND	28

Table 1: Analysis Visits

Parameter	Analysis Phase	Scheduled Day ^a	Time Interval (label on output)	Time Interval ^a (Day)	Target Time Point ^a (Day)
Patient Stated-choice Preference	OP/MA	22	Week 4 (OP/MA)	1 to end of OP/MA	22
Nasal exam	IND	1	Baseline	≤ 1	1
		28	Day 28 (IND)	2 to end of IND	28
		IND final visit	End Point (IND)	2 to end of IND	
Vital Signs: Temperature (TEMP) (IND [predose], OP/MA [predose]), Blood Pressure (BP) ^b , Hear Rate (HR), Respiratory (RESP) (IND [predose, 40M, 1H, 1H30M], OP/MA [predose, 40M, 1H])	IND	1	Baseline	≤ 1 / predose	1
			Day 1 (IND): 40M		
			Day 1 (IND): 1H		
			Day 1 (IND): 1H30M		
		4	Day 4 (IND): Predose	2 - 6	4
			Day 4 (IND): 40M		
			Day 4 (IND): 1H		
			Day 4 (IND): 1H30M		
		8	Day 8 (IND): Predose	7 - 9	8
			Day 8 (IND): 40M		
			Day 8 (IND): 1H		
			Day 8 (IND): 1H30M		
		11	Day 11 (IND): Predose	10 - 13	11
			Day 11 (IND): 40M		
			Day 11 (IND): 1H		
			Day 11 (IND): 1H30M		
		15	Day 15 (IND): Predose	14 - 16	15
			Day 15 (IND): 40M		
			Day 15 (IND): 1H		
			Day 15 (IND): 1H30M		
		18	Day 18 (IND): Predose	17 - 20	18

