6.3. Vital Signs, Weight, and BMI

Descriptive statistics for values and changes from Baseline values (described in Section 2.2) at each scheduled time-point during the induction and optimization/maintenance phases will be presented for temperature, systolic blood pressure, diastolic blood pressure, pulse rate, respiratory rate, oxygen saturation, weight, and BMI. Baseline will be used for change summaries and to determine abnormal values during all treatment phases (IND and OP/MA). Graphical presentations will be provided.

In addition, descriptive statistics of pulse rate and blood pressure (systolic and diastolic) values and changes and percent changes from predose will be provided for each intranasal dosing day.

The proportion of subjects who have a treatment-emergent abnormality, as defined in Table 4 below, during each treatment phase will be presented. A listing of subjects meeting any of the following criteria during each treatment phase will also be provided.

Table 4: Treatment-Emergent Abnormality Categories for Vital Signs

Vital Parameter	Post-baseline value outside of normal limit if:	
	Abnormally low	Abnormally high
Pulse (bpm)	A decrease from Baseline of ≥ 15 to a value ≤ 50	An increase from Baseline of ≥ 15 to a value ≥ 100
Systolic BP (mmHg)	A decrease from Baseline of ≥ 20 to a value ≤ 90	An increase from Baseline of ≥ 20 to a value ≥ 180
Diastolic BP (mmHg)	A decrease from Baseline of ≥ 15 to a value ≤ 50	An increase from Baseline of ≥ 15 to a value ≥ 105

BP = blood pressure; Baseline is defined in Section 2.2.

The proportion of subjects who experienced treatment-emergent acute hypertension (systolic BP ≥ 180 or diastolic BP ≥ 110) at any time during each treatment phase will be summarized by hypertension status.

Mean (+/-SE) values for systolic BP, diastolic BP and heart rate will be summarized by hypertension status and presented graphically for each treatment phase. In addition, for subjects with hypertension who receive antihypertensive medication, the same tables and graphs will be summarized by medication type (beta-blockers, all other agents).

A listing of subjects with oxygen saturation less than 93% will be provided.

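### When a session is postponed and the failed attempt lies nearer the target day, the SAP window rule selects the undosed visit instead of the real dosing session

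*SAP*

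**What the plan says.** **Protocol.** Section 6.1 deals with a predose blood pressure that stays above the limit after rest and repeat measurement (140/90 mmHg under age 65, 150/90 mmHg from age 65): "then dosing should be postponed and the subject scheduled to return on the following day or within the given visit window". Section 9.2 foresees that the scheduled visit has already begun when this decision is taken. It then requires, for vital signs, ECG, C-SSRS, MOAA/S and pulse oximetry, that "all time points (including predose) of the following assessments must be repeated on the actual intranasal treatment session day". The Time and Events Schedules allow ±1 day for induction visits after Day 1. For optimization/maintenance (OP/MA) they state "Visit window: ±3 days".

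**SAP.** Section 2.3 assigns visits to windows: "If a subject has 2 or more scheduled or unscheduled visits in one visit window, the visit closest to the target day will be used". Its tie rule is: "If 2 actual visits are equidistant from the target day within a visit window, the later visit is used". Neither sentence asks whether a dose was given, and postponed sessions are not mentioned. In Table 1 the vital-sign rows of a session, such as "Day 8 (IND): Predose" and its 40-minute, 1-hour and 1.5-hour companions, share one window. Section 6.3 summarises vital signs and oxygen saturation at scheduled time points against Baseline. It adds, for pulse and blood pressure only, that "changes and percent changes from predose will be provided for each intranasal dosing day". Section 6.6.2 summarises MOAA/S at scheduled time points.

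**The concern.** A postponed session leaves two visits in one window: a failed attempt with predose readings only, and the real session with the full profile. A rule that sees only calendar distance can keep the first and discard the second.

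Postdose effects on heart rate, blood pressure, respiratory rate and oxygen saturation are a named primary objective. When the postponement is for blood pressure, the trigger is one of the variables being summarised, so the affected sessions are not a random subset. They belong to subjects whose pressure had just been too high to dose. Under a by-visit selection, postdose summaries would lean low. Under either selection, predose summaries would lean high.

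**Working it through.** **1. Do both visits share a window?** The inputs are the protocol windows (±1 day in induction, ±3 days in OP/MA) and the Table 1 vital-sign windows: Day 4 = 2-6, Day 8 = 7-9, Day 11 = 10-13, Day 15 = 14-16, Day 18 = 17-20, Day 22 = 21-23, Day 25 = 24 to end of phase; OP/MA 2-11, 12-18, 19-25, then target ±3. Every protocol window lies inside its Table 1 window, so the two visits always compete. Day 1 is not exposed, because day counting starts at the first dose.

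**2. Which visit wins?** Let a be the failed attempt and b the later real session, both in days from target. The undosed visit wins when |a| < |b|; a tie goes to b.

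| Phase | Possible (a, b) | Undosed visit wins | Count |
|---|---|---|---|
| Induction, ±1 | 3 | (0,+1) | 1 of 3 |
| OP/MA, ±3 | 21 | (-2,+3), (-1,+2), (-1,+3), (0,+1), (0,+2), (0,+3), (+1,+2), (+1,+3), (+2,+3) | 9 of 21 |

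For next-day returns the counts are 1 of 2 and 3 of 6. With the failed attempt exactly on target, the undosed visit wins in 1 of 1 and 3 of 3. These count patterns; they are not expected frequencies. If only dosed visits could fill the window, the count would be 0 of 24.

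**3. What does each reading do?** Take invented values: Day 8 predose systolic 148, no dose; Day 9 predose 132, dosed, 158 at 40 minutes.

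- By visit, or by parameter: Day 8 is kept. The table has a predose value of 148 and no postdose value.
- By time point: predose comes from Day 8 and postdose from Day 9. The apparent change is 158 - 148 = +10, against a true 158 - 132 = +26.

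**4. How often could it happen?** The documents give no postponement rate. A rough guide comes from the Phase 2 peak systolic figures in Protocol 1.1.2.3. Predose mean = peak - increase. Predose variance = SDpeak² - SDincrease², which assumes that the rise is uncorrelated with the predose value.

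| Arm (n, Period 1) | Predose mean | Predose SD | P(>140) |
|---|---|---|---|
| Placebo (33) | 124.2 - 5.4 = 118.8 | √(11.51² - 7.84²) = 8.4 | 0.6% |
| 28 mg (11) | 131.8 - 10.4 = 121.4 | √(15.49² - 10.44²) = 11.4 | 5.2% |
| 56 mg (11) | 130.4 - 11.2 = 119.2 | √(18.64² - 15.01²) = 11.1 | 3.0% |
| 84 mg (12) | 146.1 - 17.1 = 129.0 | √(19.9² - 15.5²) = 12.5 | 18.9% |

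Weighted by n, the mean is 121.1, the within-arm variance 104.4 (SD 10.2) and the between-arm variance 14.4, so the total SD is √118.8 = 10.9. Under normality, P(>140) is 3.2% with SD 10.2 (z = 1.86) and 4.2% with SD 10.9 (z = 1.73). Averaging the four arm-specific tails by n gives 5.0%. The range is therefore 3-5% of single readings.

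**5. How far could a by-visit mean move?** If a share q of delivered sessions is lost and their mean postdose value exceeds that of the kept sessions by d, the reported mean is low by q × d. A redosed subject under 65 has predose systolic at most 140, and kept sessions average about 120, so d is at most about 20 mmHg if the rise does not depend on predose pressure. With q = 5%, every attempt on target and every subject redosed, the shift is at most 0.05 × 20 = 1 mmHg.

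**The case against.** A reader might infer that the rule always selects the undosed visit. It does not: an attempt before the target followed by a session at least as close keeps the dosed session, and ties go to the later visit.

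A reader might also infer that postdose data are certainly lost. Table 1 lists predose and each postdose vital-sign time point as separate rows. An undosed visit has nothing to put in a postdose row, so filling row by row loses no postdose value. The SAP does not state the level of selection, so loss is one of two possible outcomes. The other, predose and postdose from different days, is also wrong.

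Third, the effect is narrower than it looks:

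- The main by-visit change is from Study Baseline, which does not use that visit's predose value.
- The separate pulse and blood pressure summary is tied to dosing days, which on its wording excludes an undosed day.
- CGADR and ECG after the entry visit are postdose only, so they are lost only if whole visits are selected.
- Under Amendment 4, MOAA/S and pulse oximetry are not required after Visit 2.4.
- Treatment-emergent vital-sign abnormalities by phase, acute hypertension at any time in a phase, the listing of saturation below 93% and TEAEs do not use the windows.

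All of this stands, and it confines the problem to by-visit tables. It does not remove it. The dosing-day wording covers only pulse and blood pressure and gives no rule for choosing the record. Respiratory rate, oxygen saturation and MOAA/S have no such protection.

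Finally, the 84 mg arm alone would suggest 19% of sessions postponed. With between-day correlation 0.5-0.8 and next-day redosing, it would suggest 8-12% of delivered sessions lost. That is not a fair estimate. Predose pressure cannot depend on the dose about to be given, the arm had 12 subjects, and the other three arms average 118.8 to 121.4. Even so, that scenario moves the mean postdose systolic pressure by only about 0.6-0.7 mmHg.

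**Conclusion.** The gap is real but bounded. As written, SAP 2.3 selects the wrong record whenever a postponed attempt is strictly nearer the target day than the real session, and no other SAP text corrects this. By-visit tables then either lack that session's postdose values or set them beside a predose value from an undosed day. For postponements triggered by blood pressure the error is selective. Dosing can also be delayed for nasal congestion or apparent intoxication, where the same mechanism applies without that selection.

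The expected distortion of by-visit means is small: at most about 1 mmHg systolic on the pooled illustration. That rests on normality, a rise independent of predose pressure, a single reading and every attempt falling on target. The 3-5% is an upper-end guide, because the protocol postpones only after repeat readings, excludes subjects above the limit at the first session and uses 150 mmHg from age 65. The documents do not support a claim that the phase-level safety conclusions are biased.

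**What to change.** Add to SAP 2.3, for session-based parameters (vital signs, MOAA/S, CGADR, pulse oximetry and postdose ECG):

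- only visits at which intranasal study drug was given can fill a window;
- predose and postdose values in a window come from the same session;
- readings from a visit at which dosing was postponed are listed separately, with a count of postponed sessions by visit.

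The same text should state whether selection is by visit, by parameter or by time point. The count would also supply the postponement rate that the documents lack. The cost is a short SAP addition and a filter on the dosing record in programming. No new data are needed, and no clinical rule changes.
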